13.10 Visit Windows

The scheduled visits will not be windowed and will be used at nominal visit value for analysis purposes. The unscheduled and early termination (ET) visit will be mapped to a scheduled visit for analysis. In order to accommodate as much data as possible for analysis, the windows in the table below have been widened compared to protocol-specified operational windows, to have no gap between them; these windows are used for analysis purposes only. Once analysis visit windows are assigned, all visits, including scheduled visits, unscheduled visits, and ET visits will be eligible for being flagged as the “analyzed record” within the analysis window; a participant’s individual analysis visit window could potentially contain more than 1

visit. In the event of multiple visits falling within an analysis window or in case of a tie, the following rules will be used in sequence to determine the “analyzed record” for the analysis visit window:

- If the data from the scheduled visit is available, then the scheduled visit data will be used.
- If there is no data from the scheduled visit is available, the data closest to the scheduled study day for that window will be used.
- If there is a tie between the data in the number of days before and after the scheduled day, the later data will be used.

Table 1A: Visit Windows for Analysis – Part A

Scheduled Visit (+/-1 window days) in protocol	Target Study Day	Study Day Window for Visit in Analysis
Day 1	Day 1 (predose)	Day 1 (predose) or last non-missing assessment before pre-dose.
Day 7	Day 7	Day 2 - Day 10
Day 14	Day 14	Day 11 - Day 17
Day 28	Day 28	>= Day 18

Table 1B: Visit Windows for Analysis – Part B

Scheduled Visit (+/-1 window days) in protocol	Target Study Day	Study Day Window for Visit in Analysis
Day 1	Day 1 (predose)	Day 1 (predose) or last non-missing assessment before predose.
Day 7	Day 7	Day 2 - Day 10
Day 14	Day 14	Day 11 - Day 17
Day 21	Day 21	Day 18 - Day 24
Day 28	Day 28	Day 25 - Day 31
Day 35	Day 35	Day 32 - Day 38
Day 42	Day 42	>= Day 39

The summary by visit will use the “analyzed records” only – at most one per participant. The data not flagged as the “analyzed record” will be included in listings. An unscheduled visit that does not fall under any analysis window will remain in the database and will be included in the listings.

[Redacted]

[Redacted]

[Redacted]

- | [Redacted]
- | [Redacted]
- | [Redacted]
- | [Redacted]
- | [Redacted]
- | [Redacted]

[Redacted]

- | [Redacted]
- | [Redacted]
- | [Redacted]
- | [Redacted]

[Redacted]

[Redacted]

[Redacted]

[Redacted]

- | [Redacted]
- | [Redacted]
- | [Redacted]
- | [Redacted]

[Redacted text block]

[Redacted text block]

[Redacted text line]

[Redacted text block]

[Redacted text block]

- [Redacted list item]
- [Redacted list item]
- [Redacted list item]

[Redacted text line]

[Redacted text block containing multiple paragraphs and bulleted lists, all obscured by black bars.]

[Redacted text block]

[Redacted]

- [Redacted]
- [Redacted]
- [Redacted]
- [Redacted]
- [Redacted]
- [Redacted]
- [Redacted]
- [Redacted]
- [Redacted]

[Redacted]

- [Redacted]
- [Redacted]
- [Redacted]
- [Redacted]
- [Redacted]
- [Redacted]
- [Redacted]
- [Redacted]
- [Redacted]
- [Redacted]
- [Redacted]
- [Redacted]
- [Redacted]
- [Redacted]
- [Redacted]
- [Redacted]
- [Redacted]
- [Redacted]
- [Redacted]
- [Redacted]
- [Redacted]
- [Redacted]

-
- | [Redacted]
 - | [Redacted]

[Redacted]

[Redacted]

- | [Redacted]
- | [Redacted]
- | [Redacted]

[Redacted]

- | [Redacted]
- | [Redacted]
- | [Redacted]
- | [Redacted]
- | [Redacted]
- | [Redacted]
- | [Redacted]
- | [Redacted]
- | [Redacted]

[Redacted]

[Redacted]

[Redacted text block containing multiple paragraphs and bulleted lists, all obscured by black bars.]

[Redacted text block]

[Redacted text block]

[REDACTED]

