11.1.9. Daily Remote Assessments

Participants will complete daily assessments using a mobile device each morning during the Treatment Period within 1 hour after IP administration. At scheduled clinic visits, the task will be performed in the clinic under observation by study staff, otherwise the participant will perform this task remotely (at home). Daily reminders will be provided to complete these assessments ([REDACTED]).

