11.2 Full Analysis Set

The Full Analysis Set will include all participants in the Safety Set with baseline and at least one postbaseline efficacy evaluation.

[REDACTED]

[REDACTED]

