13.9 Treatments

13.9.1 Extent of Investigational Product Exposure and Treatment Adherence

The following analyses will use the Safety Set.

Total drug exposure (in mg) is defined as the total investigational product in mg for SAGE-718 that was taken during the study.

Total exposure duration to investigational product (in days) is defined as the date of last dose – date of first dose + 1. Note that this does not exclude days when the dose has been missed

The percentage of the planned exposure received is defined as the total drug exposure, divided by planned exposure, times 100. For participants who complete the treatment period, planned drug exposure is the number of days of treatment planned times 3 mg. For participants who discontinued the treatment early, the planned drug exposure is the number of days (last dose date – first dose date + 1), times 3 mg.

Investigational product adherence (%) is defined as the number of tablets taken, divided by the number of tablets planned to be taken, times 100. The schedule of investigational product is six tablets per day.

The number of tablets planned to be taken is defined as follows:

- If the participant discontinues treatment within Day 2 and Day 14 (both inclusive), the number of tablets planned to be taken is the last dose day of investigational product × 6.
- If the Part A participant does not discontinue treatment, the number of tablets planned to be taken is 84 (6x14) whereas for Part B it is 168(6x28).

Investigational product exposure and adherence will be summarized descriptively and listed. The number and percentage of participants with investigational product adherence in categories(<80%, 80-100%, >100%) will be provided. Investigational product accountability will be listed.

All investigational product exposure data will be in by-participant listings, as well as a summary of treatment adherence.

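### Despite the SAP's no-gap statement, no analysis window covers Day 1 after dosing; separately, the planned-tablet rule omits a Day 1 stop and Part B stops on Days 15–28

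*SAP*

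**What the plan says.** SAP 13.10 treats two kinds of record differently. For planned visits: "The scheduled visits will not be windowed and will be used at nominal visit value for analysis purposes". For the others: "The unscheduled and early termination (ET) visit will be mapped to a scheduled visit for analysis". The mapping uses Tables 1A (Part A) and 1B (Part B), and the section states that "the windows in the table below have been widened compared to protocol-specified operational windows, to have no gap between them".

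In Part A the Day 1 row takes "Day 1 (predose) or last non-missing assessment before pre-dose", and Part B has the same rule. In both tables the next row, Day 7, takes Day 2 to Day 10. Later rows follow on to an open-ended last row. By-visit summaries use only the one record flagged per participant in each window. For a record that fits nowhere: "An unscheduled visit that does not fall under any analysis window will remain in the database and will be included in the listings".

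SAP 13.9.1 defines adherence as tablets taken over tablets planned. The planned count has two branches. The first opens "If the participant discontinues treatment within Day 2 and Day 14 (both inclusive" and sets the count at last dose day × 6. The second gives participants who do not discontinue 84 tablets in Part A and 168 in Part B. The same section defines planned exposure in milligrams for any early stop as the inclusive number of days from first to last dose × 3 mg, with no limit on the day.

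**The concern.** The no-gap property fails at a time that matters for tolerability. The first dose is taken in the clinic under staff observation (Protocol 7.1.3 and 9.4). The notes to Protocol Tables 2 and 4 place scheduled vital signs, ECG and blood draws before dosing. A measurement prompted by a reaction to the first dose would therefore normally be unscheduled and postdose, which is the kind of record left without a window. Change from baseline in vital signs, laboratory analytes and ECG is the secondary endpoint (Protocol 6.2.2), so the gap falls within a declared endpoint of a study whose primary objective is safety and tolerability.

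The tablet rule is a separate defect. It determines the adherence percentage and its reporting categories, not which measurements are analysed. Its Day 14 limit suits Part A's treatment length and does not reach the end of Part B.

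**Working it through.** **1. The plan's own figures.** Six tablets a day gives 6 × 14 = 84 for Part A and 6 × 28 = 168 for Part B. Both reproduce.

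**2. Window coverage.** Each postdose study day was placed against the rows of Tables 1A and 1B.

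| Postdose time | Part A row | Part B row |
|---|---|---|
| Day 1 after dosing | none | none |
| Days 2–10 | Day 7 | Day 7 |
| Days 11–17 | Day 14 | Day 14 |
| Days 18–24 | Day 28 (open from Day 18) | Day 21 |
| Days 25–31 | Day 28 | Day 28 |
| Days 32–38 | Day 28 | Day 35 |
| Day 39 on | Day 28 | Day 42 |

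Day 1 after dosing is the only uncovered postdose time in either part, and no windows overlap.

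**3. Where a Day 1 postdose unscheduled or ET value goes.**
- It cannot be baseline, which must precede the first dose (SAP 13.1 and 16.0).
- It has no window, so it cannot be the flagged record, and by-visit summaries exclude it.
- PCS displays for hematology, chemistry and liver tests are by time point (SAP 16.2), and this value has none.
- PCS summaries for vital signs (16.4), ECG (16.5) and the liver thresholds (16.2) count occurrence at any post-baseline visit. They are not expressly limited to flagged records, but the SAP does not say whether an unwindowed value counts.
- It is listed.

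**4. What a wider window would change.** SAP 13.10 prefers scheduled data, then the record nearest the target day. A Day 1 value is |7 − 1| = 6 days from the Day 7 target, while any value from Days 2–10 is at most |7 − 2| = 5 days away. The Day 1 value would therefore be used only where nothing else exists in the window for that measure.

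**5. Tablet rule.** The discontinuation days with no branch are:
- Part A: Day 1, which is 1 of 14 days.
- Part B: Day 1 and Days 15–28, which is 1 + 14 = 15 of 28 days.

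The milligram rule covers these days. A Day 1 stop gives 1 × 3 = 3 mg, which equals 6 tablets of 0.5 mg. A Part B stop with last dose on Day 20 gives 20 × 3 = 60 mg, which equals 20 × 6 = 120 tablets. If a programmer filled the hole with the full-course count, a participant who missed no dose before stopping would score 6/84 = 7.1% or 6/168 = 3.6% for a Day 1 stop, and 120/168 = 71.4% for the Day 20 stop. All three fall in the category below 80%. With last dose day × 6 each scores 100%. The SAP does not prescribe the full-course count here; it prescribes nothing.

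**6. Scale.** One participant is 1/11 = 9.1% of Part A or 1/22 = 4.5% of Part B. The documents give no expected frequency of Day 1 postdose unscheduled or ET records.

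**The case against.** The strongest reply is that a first-day reaction is already captured where tolerability is judged, and most of that reply stands. SAP 16.1 counts adverse events with onset on or after the first-dose date. A Day 1 stop also appears in disposition, in the discontinuation tables and in milligram exposure. Values that the investigator judges clinically significant enter the adverse event displays. Protocol 8.4.1 invites participants who stop treatment to attend the remaining Treatment Period visits, and an ET visit on Days 2–10 maps to Day 7. A reader might infer that a same-day stop is missing from every post-baseline summary, but the documents do not support that.

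A reader might also infer that Day 1 data are relabelled as predose for every dosed participant, because "Participants will complete daily assessments using a mobile device each morning during the Treatment Period within 1 hour after IP administration" and the nominal Day 1 row is a predose row. No rule says so. SAP 14.2.2 also models remote assessments by day instead of visit, and SAP 14.1 is redacted, so the handling of daily tasks cannot be called wrong or absent. For the same reason nothing follows about the Full Analysis Set, defined as "all participants in the Safety Set with baseline and at least one postbaseline efficacy evaluation": which evaluations count is not visible.

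Assumed same-day stop risks of 0.5%, 1% and 2% give chances of 15%, 28% and 49% of at least one stop among 33 participants, from 1 − (1 − p)^33. These are chances of a stop, not of a lost record, and the risks are not from the documents.

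On tablets, the rule distinguishes the day of discontinuation from the last dose day, so one dose followed by discontinuation recorded on Day 2 does give 1 × 6. That narrows the Day 1 hole but leaves Part B after Day 14 open.

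Finally, it is defensible to keep an acute value out of a one-week summary. But the SAP should then say so, not claim that there is no gap.

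**Conclusion.** The point holds in a limited form. The no-gap statement is contradicted by both window tables at Day 1 after dosing. Unscheduled and ET safety values from that time reach listings, but not the by-visit change-from-baseline summaries or the by-time-point laboratory PCS displays. The primary endpoint is not affected. The numerical effect should be rare and small: it needs such a record on Day 1 after dosing, and a by-visit summary would change only if the participant has no other value for that measure in the window. The adherence hole is separate and wider, at 1 of 14 possible discontinuation days in Part A and 15 of 28 in Part B.

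This assumes that the redacted text after Tables 1A and 1B adds no Day 1 postdose window for safety measurements, and that recorded times separate predose from postdose values.

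**What to change.** - **Tables 1A and 1B:** for unscheduled and ET records, start the first post-baseline window at Day 1 postdose, for example Day 1 postdose to Day 10. Scheduled Day 7 data still take precedence.
- **SAP 16.2, 16.4 and 16.5:** state that any value after the first dose on Day 1 counts as post-baseline in all PCS and PCS-change summaries.
- **SAP 13.9.1:** apply last dose day × 6 to discontinuation on any day, Day 1 to Day 14 in Part A and Day 1 to Day 28 in Part B. This brings the tablet and milligram rules into line.

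The cost is a few words of SAP text and a small programming change, with no new data. There is one downside: where nothing else falls in the window, an acute Day 1 value is summarised under Day 7, which a footnote can mark. In Part B, ECG and laboratory tests are not scheduled on Day 7, so that row would hold only unscheduled or ET values. The same is already true of such values from Days 2–10, and the SAP should say whether the row is shown.

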The number and percentage of participants with potentially clinically significant (PCS) values will be provided in separate displays in hematology, serum chemistry, and liver function tests provided for such occurrence by time point.

PCS values will be identified for specific laboratory parameters as outlined in Table 5.

Liver function tests will be monitored closely for PCS values, and will be summarized for an occurrence at any post-baseline visit for the following parameters for these PCS threshold (for conditions involving more than one parameter, the results need to be from the same timepoint):

Alanine Aminotransferase: >3xULN, >5xULN, >10xULN
 Aspartate Aminotransferase: >3xULN, >5xULN, >10xULN
 Alanine Aminotransferase or Aspartate Aminotransferase: >3xULN, >5xULN, >10xULN
 Alkaline Phosphatase: >1.5xULN, >2xULN
 Total Bilirubin: >1.5xULN, >2xULN
 Total Bilirubin > 2xULN **AND** (Alanine Aminotransferase or Aspartate Aminotransferase >3xULN)
 Total Bilirubin >2xULN **AND** Alkaline Phosphatase >2xULN **AND** (Alanine Aminotransferase or Aspartate Aminotransferase >3xULN)

Any lab results considered clinically significant by the investigator will be captured as adverse events, and hence will show up in AE displays.

Pregnancy test results will be listed.

Table 5 Potentially Clinically Significant Values for Specific Laboratory Parameters

Laboratory Parameter	Gender	Units	Criteria for PCS Values (Observed values)	
			High	Low
Hematology				
Hemoglobin	Male	g/L	>185	<115
	Female	g/L	>170	<100
Hematocrit	Male	Fraction of 1	>0.55	<0.385
	Female	Fraction of 1	>0.49	<0.345
Platelet count		10 ⁹ /L	>600	<125
White blood cell		10 ⁹ /L	>15	<2.5
Basophils		10 ⁹ /L	>0.5	NA
Eosinophils		10 ⁹ /L	>1.5	NA
Neutrophils		10 ⁹ /L	NA	<1.5
Lymphocytes		10 ⁹ /L	>6.0	<0.5
Monocytes		10 ⁹ /L	>1.4	NA

Laboratory Parameter	Gender	Units	Criteria for PCS Values (Observed values)	
			High	Low
Serum Chemistry				
Albumin		g/L	>70	<28
Blood urea nitrogen		mmol/L	>10.71	NA
Calcium		mmol/L	>2.75	<2.0
Chloride		mmol/L	>120	<90
Creatinine		mmol/L	>3xULN or >3x Baseline	
Gamma Glutamyl Transferase			>3xULN	
Glucose		mmol/L	>13.9	<2.8
Sodium		mmol/L	>150	<132
Potassium		mmol/L	>5.4	<3.3
Protein		g/L		<45
Bicarbonate		mmol/L	>34	<18
Phosphorus		mmol/L	>1.94	<0.61
Liver Function Tests (LFT)				
Bilirubin		µmol/L	>2xULN	NA
Aspartate Aminotransferase		U/L	>3xULN	NA
Alanine Aminotransferase		U/L	>3xULN	NA
Alkaline Phosphatase		U/L	>1.5xULN	NA

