16.4 Vital Signs

Vitals for the following parameters - respiratory rate (breaths/minute), oral temperature (degrees C), supine heart rate (beats/minute), supine systolic blood pressure (mmHg), supine diastolic blood pressure (mmHg), standing heart rate (beats/minute), standing systolic blood pressure (mmHg), standing diastolic blood pressure (mmHg), – are collected at Screening and on Days -7, -1, 1, 7, 14, and 28 for Part A, and for Part B an additional collection will be made on Days 21, 35 and 42. Descriptive summaries of observed values and changes from baseline will be provided for vital sign parameters along with body weights by scheduled assessment time points for Part A and Part B separately. Additionally, the number and percentage of participants with PCS and potentially clinically significant change (PCSC) values will be summarized for such occurrence at any post-baseline visit. Potentially clinically significant values will be identified for vital sign parameters as outlined in Table 6.

Table 6 Potentially Clinically Significant Values and Change for Vital Sign Parameters

Vital Sign	Units	Criteria for PCS Values (Observed values)		Criteria for PCSC values (Change from Baseline values)	
		High	Low	Increase	Decrease
Heart rate (supine and standing)	Beats/min	>120	<40	NA	NA
Systolic Blood Pressure (supine and standing)	mmHg	>180	<90	≥30	≥30
Diastolic Blood pressure (supine and standing)	mmHg	>110	<50	≥20	≥20
Supine - Standing Systolic Blood Pressure	mmHg	≥20			
Supine – Standing Diastolic Blood Pressure	mmHg	≥10			
Orthostatic hypotension: supine – standing SBP and DBP	mmHg	SBP ≥20 and DBP ≥10			
Possible Orthostatic hypotension: supine – standing SBP and DBP	mmHg	SBP ≥20 or DBP ≥10			

The orthostatic vital sign - the change from supine to standing (Supine – Standing) in heart rate, systolic and diastolic blood pressure – will be summarized by scheduled assessment timepoint, at 1 and 3 minutes.

Any vital signs result considered clinically significant by the investigator will be captured as adverse events, and hence will show up in AE displays. All vital sign assessments along with PCS will be listed.

16.5 12-Lead Electrocardiogram

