Supine 12-lead ECGs will be performed in triplicate, and are collected on screening, days -1, 1, 7, 14, and 28 for Part A whereas for Part B it is performed on days -1, 14, 28, and 42. The following ECG parameters will be listed for each participant: heart rate (beats per minute), PR (msec), QRS (msec), QT (msec), and QTcF (msec).

The average of the triplicate values will be used in the summary, including baseline ECG values. The precision on averages is to keep only 2 decimal places. The observed value at each time point and change from baseline at each post-baseline scheduled time point will be summarized. Each ECG is evaluated as 'normal', 'abnormal, not clinically significant' and 'abnormal, clinically significant'; the number and percentage of participants with at least one of the triplicate values in the categories of normal, 'abnormal, clinically significant' and 'abnormal, not clinically significant' will be provided at baseline and each post-baseline scheduled assessment time point.

The number and percentage of participants with PCS and PCSC values will be summarized for such occurrence of baseline and at any post-baseline visit. Potentially clinically significant values will be identified for ECG parameters as outlined in Table 7. A listing of ECG and QTcF PCS values will be provided.

Table 7 Potentially Clinically Significant Values and Change for ECG Parameters

ECG	Units	Criteria for PCS Values (Observed values)		Criteria for PCSC values (Change from Baseline)	
		High	Low	Increase	Decrease
QTcF Interval	msec	>450 but <=480 >480 but <=500 >500	NA	>=30 to 60 >60	NA

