19.0 Appendix

19.1 Appendix-A Schedule of Study Assessments (Part A)

Study Period	Screenin g	Baseline		Treatment			Follow Up		
	D -21 to D -8	D -7 (±1 d)	D -1	D 1	D 4 ^a	D 7 (±1 d)	D 14 or ET	D 21 ^a (±1 d)	D 28 (±2 d)
Informed consent ^b	X								
Inclusion/exclusion criteria	X	X	X						
Medical history and demographics ^c	X								
Bodyweight	X			X		X	X		X
Body height	X								
Hoehn and Yahr staging	X								
Montreal Cognitive Assessment	X								
Test of Premorbid Functioning	X								
Vital signs ^d	X	X	X	X		X	X		X
Physical examination ^e	X	X	X				X		
EEG ^f	X								
12-lead ECG ^g	X		X	X		X	X		X
C-SSRS ^h	X	X	X	X		X	X		X
Clinical laboratory tests ⁱ	X		X			X	X		X
Alcohol test ^j	X	X							
Urine drug test	X	X	X	X		X	X		
FSH test ^k	X								
Pregnancy test ^l	X		X				X		X
Serology test ^m	X								
Participant training ^o		X	X						

Study Period	Screening	Baseline		Treatment				Follow Up	
Study Day	D -21 to D -8	D -7 (±1 d)	D -1	D 1	D 4 ^a	D 7 (±1 d)	D 14 or ET	D 21 ^a (±1 d)	D 28 (±2 d)
Remote assessments ^t				X					
IP self-administration ^u				X (once daily)					
IP dispensation ^v				X		X			
IP accountability ^w				X					
Safety telephone call					X			X	
TEAEs/SAEs				X					
Concomitant medications ^x				X					

Abbreviations: C-SSRS = Columbia–Suicide Severity Rating Scale; d = days; ECG = electrocardiogram; EEG = electroencephalogram; ET = early termination; FSH = follicle stimulating hormone; IP = investigational product; SAE = serious adverse event; TEAE = treatment-emergent adverse events;

Note: In the event of early termination, efforts should be made to collect the Day 14 visit assessments. When scheduled for the same time point, procedures should be performed in the following order: vital signs, ECG, blood draws, morning meal, IP dosing, then any scheduled postdose and/or

In the setting of public health advisories or similar risks to patient safety, assessments scheduled to be conducted at the study site may be performed via telephone/video if feasible. For assessments that cannot be conducted by phone or video, an in-home visit may be conducted.

a Day 4 and Day 21 visits will occur via scheduled telephone calls.

b Both participants and caregivers are to be consented during the Screening Period.

c In addition to full medical history, all nonpharmacological methods (eg, psychosocial, psychotherapeutic) used to treat or prevent neuropsychiatric, functional, and cognitive manifestations of PD are to be recorded.

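### Hematology PCS counts (and, by the SAP text, non-liver chemistry) can omit a value from a displaced unscheduled or early-termination test; separately, the protocol's laboratory shift summary is missing without being declared

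*SAP*

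**What the plan says.** **Record selection (SAP 13.10).** "The unscheduled and early termination (ET) visit will be mapped to a scheduled visit for analysis". When several records fall in one window the rules apply in order, and the first is "If the data from the scheduled visit is available, then the scheduled visit data will be used". Only if there is no scheduled record does the one nearest the target day count. By-visit summaries use the selected records, "at most one per participant"; the others go to listings.

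**PCS counts.** SAP 16.2 gives the number and percentage of participants with PCS values "in separate displays in hematology, serum chemistry, and liver function tests provided for such occurrence by time point". For liver tests alone it adds a count that "will be summarized for an occurrence at any post-baseline visit". Vital signs (SAP 16.4) have the same kind of count: "will be summarized for such occurrence at any post-baseline visit". So does QTcF (SAP 16.5): "will be summarized for such occurrence of baseline and at any post-baseline visit". In SAP Appendix G the hematology PCS tables (14.3.3.1.2A/B) are titled by timepoint; the biochemistry PCS tables (14.3.3.2.2A/B) are not.

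**ET laboratory tests are planned.** The Part A schedule in the SAP states: "In the event of early termination, efforts should be made to collect the Day 14 visit assessments". The Part B schedule asks for the Day 28 assessments. Both sets include clinical laboratory tests.

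**Shift.** Protocol 13.6.2 promises, besides PCS summaries, a baseline-to-postbaseline shift in the abnormality of laboratory results. SAP 16.2 contains no shift, and SAP 6.1 declares one change from the protocol only, a medication summary table.

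**The concern.** Safety and tolerability is the primary objective, and change in laboratory analytes is part of the secondary endpoint. PCS tables exist to show whether anyone crossed a fixed numeric limit. A count confined to one scheduled-first record per window can show zero when a participant did cross the limit, at a test prompted by symptoms or done on leaving the study. Liver tests, vital signs and QTcF have an any-post-baseline count that would catch this if it uses all records. Hematology has none, and neither does non-liver chemistry by the SAP text.

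The shift omission is a separate matter. A promised output has gone without a declared reason, so no planned table shows movement between normal and abnormal. PCS counts are no substitute, because many PCS limits are fixed values or multiples of the upper limit of normal (ULN), not the limits of the normal range.

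**Working it through.** **1. Denominators.** The plan's total is 30 completers at 10% dropout: 30/0.9 = 33.3, stated as approximately 33. By part, 10/0.9 = 11.1 and 20/0.9 = 22.2, stated as 11 and 22. The stated figures reproduce to within rounding.

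**2. Which ET tests lose their place.** Windows are from SAP Tables 1A and 1B. Post-baseline laboratory days are from SAP 16.2: Days 7, 14 and 28 (Part A); Days 14, 28 and 42 (Part B). Scheduled visits are assumed to fall on their target days, and the participant has no further scheduled tests after ET.

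| Part | ET test on | Window | Scheduled lab already in window | Result |
|---|---|---|---|---|
| A | Days 2–6 | 2–10 | none | selected |
| A | Days 8–10 | 2–10 | Day 7 | displaced |
| A | Days 11–13 | 11–17 | none | selected |
| A | Days 15–17 (follow-up) | 11–17 | Day 14 | displaced |
| A | Days 18–27 (follow-up) | 18 onward | none | selected |
| B | Days 2–10 | 2–10 | none planned | selected |
| B | Days 11–13 | 11–17 | none | selected |
| B | Days 15–17 | 11–17 | Day 14 | displaced |
| B | Days 18–24 | 18–24 | none planned | selected |
| B | Days 25–27 | 25–31 | none | selected |
| B | Days 29–31 (follow-up) | 25–31 | Day 28 | displaced |
| B | Days 32–38 (follow-up) | 32–38 | none planned | selected |
| B | Days 39–41 (follow-up) | 39 onward | none | selected |

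On treatment, 3 of 14 days are exposed in Part A and 3 of 28 in Part B. The ±1-day allowance on the Day 7 visit (Part A) and the Day 14 visit (Part B) changes 3 to between 2 and 4. In Part B, an ET test in the Day 7, 21 or 35 window is selected, but the SAP does not say whether a PCS table would show a time point with no scheduled laboratory test.

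**3. Unscheduled tests.** These can be displaced in any window that has a scheduled laboratory test: all three post-baseline windows in Part A (Day 2 onward), and the Day 14, 28 and 42 windows in Part B. With no scheduled record, one unscheduled test can displace another. For target Day 28, a PCS value on Day 25 (3 days away) loses to a normal value on Day 29 (1 day away).

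**4. Illustration.** SAP Table 5 sets the low platelet limit at <125 ×10⁹/L. The platelet values here are invented.
- Part A: scheduled Day 7 = 150, ET Day 9 = 110. Both lie in Days 2–10, so Day 7 is selected and the count is 0 of 11 where an all-records count gives 1 of 11.
- Part B: the same values on scheduled Day 14 and ET Day 16 (Days 11–17) give 0 of 22 instead of 1 of 22.
- If the scheduled value is itself PCS, that participant is still counted.

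**5. Size of one missed participant** (exact 95% intervals).

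| | By-time-point rule | All records |
|---|---|---|
| Part A | 0/11 = 0% (0 to 28.5%) | 1/11 = 9.1% (0.2 to 41.3%) |
| Part B | 0/22 = 0% (0 to 15.4%) | 1/22 = 4.5% (0.1 to 22.8%) |

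**6. Shift.** Protocol 13.6.2 promises it. SAP 16.2 gives descriptive statistics and PCS counts, and uses normal ranges for low/high flags in listings and for ULN-multiple PCS thresholds. The laboratory tables in Appendix G run from 14.3.3.1.1 to 14.3.3.3.2 without a numbering gap, and none is a shift table. The relevant text is readable, so redaction does not explain the absence.

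**The case against.** **The SAP never says that a PCS display is a by-visit summary under 13.10.** True: the exclusion comes from reading 13.10 and 16.2 together, and Appendix G gives titles only, so an overall row in the hematology table cannot be ruled out. But a count by time point in a table titled by timepoint is most naturally programmed on the selected records, and nothing asks for an overall row. The statement in SAP 13.1 that all non-missing data are used is a general one about missing data; 13.10 is the specific rule for choosing records.

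**Chemistry is less certain.** This stands. The biochemistry PCS title does not mention time points, and Appendix G lists no separate liver PCS table, so that table may carry the liver counts made at any post-baseline visit. What is established is a mismatch between text and title.

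**The values are not lost.** This also stands. Displaced results are listed, which is manageable for about 33 participants. Under Protocol 12.2.1 and SAP 16.2 they become adverse events if the investigator judges them clinically significant or if, for example, they lead to interruption, discontinuation or medical treatment. A value that meets a PCS limit but no adverse-event criterion would be seen only in a listing.

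**Stronger readings to avoid.** A reader might infer that ET laboratory tests are dropped in general; the table in the working shows that most ET days are kept. A reader might put two affected participants in Part A (2/11 = 18.2%), but the plan expects one dropout there (11 − 10 = 1), so this would need unscheduled tests that the documents do not quantify. A reader might also infer that normal ranges serve only for listing flags; SAP 16.2 tabulates PCS counts on multiples of ULN as well.

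**Conclusion.** Both points hold, within limits.

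(1) As written, the plan can leave a hematology PCS value out of the PCS table when it occurs at an unscheduled or ET test and a non-PCS scheduled value shares its window. The same applies to non-liver chemistry if the SAP 16.2 text governs. The number affected is unknown and probably very small; each one is worth 9.1 percentage points in Part A or 4.5 in Part B. This assumes the planned numbers dosed, and that by-time-point PCS counts follow the analyzed-record rule. Liver tests, vital signs and QTcF are covered if their any-post-baseline counts use all records. That is the natural reading, but the SAP does not state it.

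(2) The promised laboratory shift summary is absent and its removal is undeclared. This does not depend on how many extra tests occur, and it covers every parameter with a normal range in both parts.

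**What to change.** 1. Add an any-post-baseline PCS row for hematology and chemistry, using all post-baseline records (scheduled, unscheduled and ET), beside the by-time-point rows.
2. State that the existing any-post-baseline counts for liver tests, vital signs and QTcF also use all records.
3. Align the hematology and biochemistry PCS table titles with the SAP 16.2 text.
4. Add the shift summary against laboratory normal ranges, or declare and justify its removal in SAP 6.1.

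The cost is SAP wording, one row in each of two PCS tables per part, and one shift summary per part (or a short entry in SAP 6.1). No new data are needed. An all-records count rises with the number of tests a participant has, so the by-time-point rows should stay and the analyzed-record rule should remain for by-visit summaries.
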